2.0 Hypothesis

We propose that consumption of the EAA/protein composition will stimulate the net gain (net protein synthesis) of body protein in a dose-dependent manner. We further propose that the magnitude of increase in net protein synthesis will be greater than induced by the consumption of the same amount of whey protein isolate, which is currently the most popular supplement on the market targeting the stimulation of muscle protein synthesis.

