3.0 Study Design and Procedures

We will study a total of up to 20 healthy male and females between 18 and 50 years of age. We will use a randomized, two-period, stable isotope (Cambridge Isotope Labs, Tewksbury, Mass.) infusion study: 4.5-hour basal fasted period and 4-hour post-meal period (total 8.5-h time period). The principal end-point will be the total anabolic response (whole body protein synthesis minus breakdown) and the secondary end point will be muscle protein fractional synthetic rate (FSR) over the 4 hours following the consumption of either the test composition or whey protein. The plasma amino acid response will also be a secondary end point.

We will utilize two distinct arms within this protocol. Arm 1 will consist of a group of subjects who will perform a randomized, single blind cross-over (two stable isotope studies) between the two doses of the EAA/protein study supplement, with a \geq oneweek washout period between stable isotope studies. Arm 2 will consist of a group of subjects (with similar gender composition) who will undergo one stable isotope study during which they will ingest the whey protein isolate study supplement. Subjects will be enrolled into the double stable isotope study arm, utilizing the specific consent form. After Arm 1 enrollment is completed, unique future subjects will be enrolled into Arm 2 – the single stable isotope arm, using the specific consent form.

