7.0 Data Analysis

7.1 Statistical Analysis plan

The purpose of this study is to estimate and compare the effect of two different nutritional beverages on total anabolic response (TAR) and muscle protein synthesis (MPS). To this end, an analysis of covariance (ANCOVA) model will be employed to compare the protein sources with respect to mean response (either TAR or MPS) after adjusting for basal measures. If a significant protein group effect is detected, then pairwise comparisons will be performed to determine if the two sources or two doses differ. In this case, the Tukey-Kramer method will be used to adjust for multiple comparisons. A 5% will be used to determine statistical significance.

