7.2 Sample Size Calculation & Power Analysis

A total of N=16 subjects will be required for this study, 8 in each arm. With this sample size, the ANCOVA model will have 80% power to detect effect sizes of $f = 0.484$ or larger (Table 1). This estimate assumes the basal covariate explains 50% of the variation in the response and a 5% α -level is used to determine statistical significance.

Table 1. Expected Effect Size by Covariate Variation

Variation Explained by Covariate (%)	Detectable Effect Size, f
10	0.649
30	0.573
50	0.484
70	0.375
90	0.216

(Note that the effect size, f , is simply the ratio of the variation between the three group means and the between-subject variation). In the event the effect of the covariate is mis-specified, the following table presents effect sizes that can be detected as the magnitude of variation explained by the covariate increases from 10% to 90%.

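### With exactly three groups and a 5% gate, the Tukey-Kramer step in section 7.1 is not needed for family error, and it costs power for the two section 2.0 claims

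*Combined protocol and SAP*

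**What the plan says.** Section 7.1 fits an ANCOVA for "mean response (either TAR or MPS) after adjusting for basal measures", at a 5% level, and then sets two steps. The first is a gate: "If a significant protein group effect is detected, then pairwise comparisons will be performed to determine if the two sources or two doses differ". The second is an adjustment: "In this case, the Tukey-Kramer method will be used to adjust for multiple comparisons".

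Section 2.0 makes two claims: that the product "will stimulate the net gain (net protein synthesis) of body protein in a dose-dependent manner", and that the size of the increase "will be greater than induced by the consumption of the same amount of whey protein isolate". Section 5.4 gives about 6.3 g and 12.6 g for the product and 12.6 g for whey. The claims therefore correspond to 12.6 g vs 6.3 g EAA/protein (dose contrast) and 12.6 g EAA/protein vs 12.6 g whey (whey contrast). Section 7.1 does not name either pair in those terms.

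Section 7.2 states: "With this sample size, the ANCOVA model will have 80% power to detect effect sizes of" 0.484 or larger, with 8 subjects per arm and a covariate that explains 50% of the variation. It describes f as "the ratio of the variation between the three group means and the between-subject variation". Under section 3.0, Arm 1 is a "randomized, single blind cross-over (two stable isotope studies) between the two doses of the EAA/protein study supplement", and different subjects receive whey in Arm 2.

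**The concern.** The gate and Tukey-Kramer guard against the same error: declaring some pair different when it is not. If one is enough, the other only raises the bar for the claims the study was set up to test. With 8 subjects per arm there is little power to spare. Section 7.2 gives power for the three-group test alone, so the plan does not show how much is lost between passing the gate and establishing either claim.

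**Working it through.** **Inputs.** Three groups, 8 per arm, f = 0.484, R² = 0.50 and α = 5% (sections 7.1 and 7.2). Arm 1 contributes two observations per person, so there are 3 × 8 = 24 observations. The pattern of means and the within-person correlation are not in the documents and are assumed below.

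**1. The plan's own figure.** Noncentrality is λ = N f²/(1 − R²) = 24 × 0.484²/0.5 = 11.24. With df 2 and 24 − 3 − 1 = 20, the critical F is 3.493 and power is 80.0%. The other four rows of Table 1 give 79.9% to 80.1%. The 80% is therefore the power of the three-group F test, with all 24 observations treated as independent.

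**2. The two thresholds at df 20.** An unadjusted pair needs |t| > 2.086. Tukey-Kramer needs |t| > 2.530, a per-pair level of 0.0199.

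**3. Why the gate is enough with three groups.** If any two of the three pairwise nulls are true, all three means are equal, and the 5% gate bounds the error. Otherwise at most one pair is truly equal, and it is tested once at 5%. Either way family error is at most 5%. The argument fails with four or more groups.

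**4. Expected t values.** With total SD 1, the residual SD is √0.5, and the SE of a difference is √0.5 × √(2/8) = 0.354.
- High dose alone differs by d: f = d√2/3, so d = 1.027 and the expected t is 1.027/0.354 = 2.90 for both claims.
- Low dose midway between whey and high dose: f = d/√6, so d = 1.186. The expected t is 3.35 for the whey contrast and half that, 1.68, for the dose contrast.

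**5. Simulated power and error** (400,000 trials per pattern, balanced covariate, df 20).

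| Assumed pattern | Quantity | Plan | Tukey-Kramer, no gate | (a) Gate, unadjusted pairs | (b) Holm, two contrasts |
|---|---|---|---|---|---|
| High dose alone differs | each claim | 64% | 65% | 73% | 74% |
| High dose alone differs | both claims | 50% | 50% | 67% | 66% |
| Low dose midway | whey contrast | 77% | 79% | 80% | 82% |
| Low dose midway | dose contrast | 22% | 22% | 35% | 35% |
| Whey alone differs | whey contrast | 64% | 65% | 73% | 69% |
| All means equal | any false rejection | 4.5% | 5.0% | 5.0% | about 4.5% (two pairs only) |
| One pair equal, third mean far away | false rejection of that pair | 2% | 2% | 5% | not compared |

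Removing only the gate adds 0 to 1.4 points. Removing only Tukey-Kramer adds up to 13 points for a single claim (22% to 35%) and 17 for both (50% to 67%).

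**6. Covariate balance.** If the basal value is randomly imbalanced across groups, absolute power is about 2 points lower (each claim 62% to 71% when the high dose alone differs). The gain is the same.

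**7. Dependence on standard errors.** If the ANCOVA ignores the Arm 1 pairing, option (a) can reach about 5.4% to 5.9% false rejection for a whey contrast at within-person correlations of 0.5 to 0.8. Under a mixed model with Satterthwaite df, the dose pair reaches up to 5.8% (at correlation 0).

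**The case against.** The strongest reply is that the plan is valid and its choice defensible. Section 7.1 aims to estimate as well as compare, and Tukey-Kramer supplies simultaneous intervals for all three pairs. Its slack also gives some protection while the pairing is unmodelled: at correlation 0.8, the planned rule falsely rejects an equal whey pair 2.3% of the time, against 5.4% under (a). Both points stand as costs of the change. The matched comparison can also be worked out from sections 2.0 and 5.4, so naming it in section 7.1 is a clarification.

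Four stronger readings are tempting and are not supported.
- A reader might infer that the plan's error rate is wrong. It is not; it is at or below 5% in the plan's model.
- A reader might infer that removing either layer helps. Only removing Tukey-Kramer does so materially. Option (b) replaces both layers, and part of its gain comes from giving up the formal 6.3 g vs whey test.
- A reader might infer that (a) never rejects less than the plan. That holds only when the model is unchanged. If whey alone differs, the planned rule in an ANCOVA that ignores pairing has 64.5% and 64.7% power for the whey contrast at correlations 0.5 and 0.8. A crossover mixed model with (a) has 62.1% and 58.4%.
- A reader might infer that section 7.2 presents the 80% as power for the section 2.0 claims. It attributes the figure to the ANCOVA model and defines f over three means. It is silent on the claims rather than wrong about them.

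**Conclusion.** The point holds as an optional improvement in efficiency. After a 5% gate on exactly three groups, Tukey-Kramer adds nothing needed for family error. In the plan's model it costs about 9 points per claim and 17 for both if the high dose alone differs. If the low dose is midway, it costs about 3 points on the whey contrast and 13 on the dose contrast. Family error moves from 4.5% to 5.0% under equal means, and from about 2% to 5% when one pair alone is equal, which is still within the stated level.

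These sizes rest on f = 0.484 (a detectable effect, not an expected one), R² = 50%, assumed mean patterns, and 24 observations treated as independent. Control is per endpoint; section 7.1 makes no adjustment across TAR and MPS. How to model the Arm 1 crossover is a separate question.

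**What to change.** In section 7.1, name the two comparisons: 12.6 g EAA/protein vs 12.6 g whey (source), and 12.6 g vs 6.3 g EAA/protein (dose). Then, separately for TAR and MPS, choose one of the following.
- **(a)** Keep the three-group test at 5% and follow it with unadjusted 5% pairwise tests. Cost: the intervals are no longer simultaneous, and the justification holds only for three groups.
- **(b)** Drop the gate, test the two named contrasts with Holm at 5%, and report 6.3 g vs whey as an estimate with a confidence interval. Cost: no formal test of that pair.

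Whichever is chosen, the standard errors must respect the Arm 1 pairing, with Kenward-Roger df or a paired test for the dose contrast, so that the 5% level is kept. State that modelling the crossover can itself lower whey-contrast power in some patterns.

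In section 7.2, label the 80% as the power of the three-group F test. All of this is SAP wording, with no added subjects, visits or samples.

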7.2 Sample Size Calculation & Power Analysis

A total of N=16 subjects will be required for this study, 8 in each arm. With this sample size, the ANCOVA model will have 80% power to detect effect sizes of $f = 0.484$ or larger (Table 1). This estimate assumes the basal covariate explains 50% of the variation in the response and a 5% α -level is used to determine statistical significance.

Table 1. Expected Effect Size by Covariate Variation

Variation Explained by Covariate (%)	Detectable Effect Size, f
10	0.649
30	0.573
50	0.484
70	0.375
90	0.216

(Note that the effect size, f , is simply the ratio of the variation between the three group means and the between-subject variation). In the event the effect of the covariate is mis-specified, the following table presents effect sizes that can be detected as the magnitude of variation explained by the covariate increases from 10% to 90%.

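### The 80% power at f = 0.484 in Section 7.2 rests on an unstated assumption of 24 independent responses; 16 of the 24 are pairs from 8 crossover subjects

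*Combined protocol and SAP*

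**What the plan says.** Section 7.2 gives the size as "A total of N=16 subjects will be required for this study, 8 in each arm" and continues: "With this sample size, the ANCOVA model will have 80% power to detect effect sizes of" f = 0.484 or larger, with a 5% significance level and a basal covariate explaining 50% of the variation. Table 1 gives detectable f for five values of that percentage. The section describes f as "the ratio of the variation between the three group means and the between-subject variation".

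Section 3.0 sets out two unlike arms. "Arm 1 will consist of a group of subjects who will perform a randomized, single blind cross-over (two stable isotope studies", comparing the two EAA/protein doses. "Arm 2 will consist of a group of subjects (with similar gender composition) who will undergo one stable isotope study", on whey. The same section allows more people than 7.2 requires: "We will study a total of up to 20 healthy male and females between 18 and 50 years of age".

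Section 7.1 plans an ANCOVA to "compare the protein sources with respect to mean response (either TAR or MPS) after adjusting for basal measures", followed by Tukey-Kramer pairwise comparisons if the group effect is significant. Neither 7.1 nor 7.2 mentions a subject effect, a repeated-measures term or a within-subject correlation.

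**The concern.** The power statement speaks of 16 subjects in two arms, while f is defined over three means, and the section does not say how many responses enter the model. If the calculation treats all responses as independent, it ignores the fact that two of the three beverages are given to the same people. This is the trial's only size justification. Without a stated correlation and pattern of means, a reader cannot tell what the 80% refers to, or whether it holds for the comparison with whey, which is between different people. The same silence in 7.1 leaves the primary model undefined for paired data.

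**Working it through.** **Inputs.** From 7.2: 16 subjects, 8 per arm, 80% power, α = 5%, R² = 50%, f = 0.484, Table 1, three means. From 3.0: two studies per Arm 1 subject, one per Arm 2 subject. Assumed, because the documents give no value: residual within-subject correlation ρ of 0.3 to 0.7, and the pattern of the three means.

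**1. Reproducing Table 1.** For an ANCOVA F test with N independent observations, k groups and one covariate, the noncentrality is λ = N f² / (1 − R²), on k − 1 and N − k − 1 df. With N = 24 and k = 3 (df 2 and 20), λ = 24 × 0.484² / 0.5 = 11.24 and power is 80.0%. Solving for f at 80% power:

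| R² | Table 1 | N = 24, k = 3 | N = 16, k = 3 | N = 16, k = 2 |
|---|---|---|---|---|
| 10% | 0.649 | 0.6491 | 0.8386 | 0.7189 |
| 30% | 0.573 | 0.5725 | 0.7396 | 0.6340 |
| 50% | 0.484 | 0.4838 | 0.6251 | 0.5359 |
| 70% | 0.375 | 0.3748 | 0.4842 | 0.4151 |
| 90% | 0.216 | 0.2164 | 0.2795 | 0.2396 |

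With three groups, N = 23 gives 0.496 and N = 25 gives 0.472 at R² = 50%. Two groups with 19 observations in total also agree with every row to within 0.001. But 19 appears nowhere in the plan, cannot be 8 per arm, and conflicts with three means. So 24 = 3 × 8 is inferred from the match; the documents do not state it.

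**2. Counting the responses.** 8 × 2 + 8 × 1 = 24. The count is right. However, 16 of the 24 are pairs from 8 people.

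**3. Power with the pairing modelled.** Take the total SD as 1, so the residual variance is 0.5. Let W be the mean of the two doses minus whey, and D the difference between the doses. Then

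λ = W² / {0.5 × [(1 + ρ)/16 + 1/8]} + D² / {0.5 × 2(1 − ρ)/8}.

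At ρ = 0 this is 11.24 for every pattern with f = 0.484. At ρ = 0.5 the two denominators are 0.1094 and 0.0625.

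- Doses alike, whey different: f² = 2W²/9, so W² = 4.5 × 0.2343 = 1.054 and D = 0. λ = 1.054 / 0.1094 = 9.64.
- Graded (12.6 g, 6.3 g, whey in equal steps d): f² = 2d²/3, so d² = 0.3514, W² = 2.25d² = 0.7906 and D² = 0.3514. λ = 7.23 + 5.62 = 12.85.
- Only 12.6 g differs: D² = 1.054 and W² = 0.2635. λ = 2.41 + 16.87 = 19.28.

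Power at f = 0.484, as df 13 / df 20:

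| Pattern | ρ = 0 | ρ = 0.3 | ρ = 0.5 | ρ = 0.7 |
|---|---|---|---|---|
| Doses alike | 76.4 / 80.0% | 72.1 / 75.9% | 69.4 / 73.3% | 66.8 / 70.7% |
| Graded | 76.4 / 80.0% | 78.0 / 81.6% | 82.0 / 85.3% | 90.1 / 92.6% |
| Only 12.6 g differs | 76.4 / 80.0% | 86.8 / 89.6% | 94.5 / 96.2% | 99.5 / 99.7% |

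Correlation lowers the first term of λ and raises the second. Modelling the pairs therefore helps the dose comparison and not the comparison with whey.

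**4. Power of the ANCOVA as written** (no subject effect, df 20; simulation, 20,000 trials per cell):

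| Pattern | ρ = 0.3 | ρ = 0.5 | ρ = 0.7 |
|---|---|---|---|
| No effect (type I error) | 4.1% | 3.8% | 3.7% |
| Doses alike | 75.5% | 74.1% | 73.1% |
| Graded | 77.3% | 77.0% | 76.3% |
| Only 12.6 g differs | 80.8% | 82.0% | 84.7% |
| Doses at extremes, whey midway | 82.6% | 85.6% | 88.6% |

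The same simulation at ρ = 0 gives about 78%, because the basal value is itself random. About 2 points of the gap from 80% are therefore not due to pairing.

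**The case against.** The plan has a fair defence. Section 7.2 refers to three means, the count of 24 is correct, and Table 1 is arithmetically right under independence. The error is an omission, and the power lies on both sides of 80%. The protocol's first hypothesis is that the product will "stimulate the net gain (net protein synthesis) of body protein in a dose-dependent manner". If that holds, the doses are not alike, and the relevant patterns give roughly 76–89% under the planned ANCOVA. All of this stands and limits the size of the point.

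A reader might infer four stronger things that the documents do not support.

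- **That true power is 57%.** This is the result for 16 independent observations in three groups (56.9%). The design yields 24 responses.
- **That the shortfall falls on a stated hypothesis.** Section 2.0 predicts superiority over the same amount of whey. It does not predict that both doses act alike, which would contradict dose dependence. Doses alike is a sensitivity case.
- **That ignoring the pairs inflates false positives.** The omnibus error is about 4%, slightly conservative.
- **That power is 62–67%, or that detectable f is 0.56–0.58.** Those doses-alike figures belong to a mixed model with Kenward-Roger df, which the plan does not specify. For the planned ANCOVA, detectable f in that case is about 0.51–0.53. Likewise, df 13 alone gives 76.4% at ρ = 0, so part of the low end of the modelled range is a df choice.

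The ceiling of 20 subjects does not answer the point. If 10 + 10 completed (an assumption), doses-alike power by the formula with df 17 would be 79–84%, but 7.2 bases its claim on 16.

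**Conclusion.** The concern holds. The 80% at f = 0.484 is correct only if the 24 responses are independent, which 7.2 does not say and Section 3.0 rules out for 16 of them unless the residual correlation is zero. At a correlation of 0.3–0.7, the planned ANCOVA falls short by about 4–7 points if the doses act alike and by about 3–4 points if the response is graded; it exceeds 80% by about 1–9 points for the other two patterns. With the pairs modelled (df 13 to 20), the ranges are about 67–76% for doses alike, 78–93% for graded, and 87% or more when only 12.6 g differs.

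These figures rest on R² = 50% as in 7.2, on the assumed correlation range and on the named patterns of means. The simulation also assumes a between-visit correlation of 0.6 for the basal value. The finding does not show that the trial is too small or that its test is invalid. It shows that the stated power is not a fixed property of this design and that the model in 7.1 is incomplete. It should be fixed, at moderate priority.

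**What to change.** Keep 8 + 8.

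1. In 7.2, state that 16 subjects give 24 responses, 8 per beverage, and that the 16 EAA/protein responses are pairs from 8 subjects.
2. Label the 80% and Table 1 as assuming independent responses. Beside them, give power or detectable f for the actual layout over a stated range of within-subject correlation, and name the pattern of means used.
3. In 7.1, specify a model with condition (three levels), basal value and a random subject effect, with a small-sample df method. Kenward-Roger is one acceptable choice.

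The cost is a rewording of 7.2 and about one sentence in 7.1, with no extra subjects, samples or endpoints. The downside is that for some patterns of means, notably where the difference is mainly from whey, the stated power will be less favourable than 80%.

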8.0 Ethical Considerations

This study will be conducted in accordance with all applicable government regulations and University of Arkansas for Medical Sciences research policies and procedures. This protocol and any amendments will be submitted and approved by the UAMS Institutional Review Board (IRB) to conduct the study.

The formal consent of each subject, using the IRB-approved consent form, will be obtained before that subject is submitted to any study procedure. All subjects for this study will be provided a consent form describing this study and providing sufficient information in language suitable for subjects to make an informed decision about their participation in this study. The person obtaining consent will thoroughly explain each element of the document and outline the risks and benefits, alternate treatment(s), and requirements of the study. The consent process will take place in a quiet and private room, and subjects may take as much time as needed to make a decision about their participation. Participation privacy will be maintained and questions regarding participation will be answered. No coercion or undue influence will be used in the consent process. This consent form must be signed by the subject and the individual obtaining the consent. A copy of the signed consent will be given to the participant, and the informed consent process will be documented in each subject's research record.

9.0 Dissemination of Data

Results of this study may be used for presentations, posters, or publications. Adesso LLC, will have 90 days to review potential publications before submission. The ultimate decisions on content of publications will reside with UAMS investigators. The publications will not contain any identifiable information that could be linked to a participant.

11.0 Appendices

11.1 CTRLAL Muscle Biopsy SOP

Policy: The following information is written to serve as a resource and guideline for the percutaneous vastus lateralis muscle biopsy procedure. This SOP will ensure that the procedure is performed in a consistent manner that protects participant safety. This procedure can be performed concurrently with a fat biopsy, provided that the protocol calls for samples at the same time-point. In this case, the fat bx shall be performed first so that the muscle bx site does not bleed during the performance of the fat bx.

Purpose: The muscle biopsy procedure is conducted to obtain a sample (~100-150mg) of muscle tissue for metabolic (and possibly structural) analyses.

Responsibility and Accountability:

Principal Investigator: Will oversee, direct, and be responsible for assuring adherence to the entire procedure.

Study Physician: Responsible for overall medical supervision and performance of the procedure including handling of subject complaints or adverse events related to muscle biopsies.

Study/staff nurse: Will assist study physician with their performance of muscle biopsy procedure. Will educate subject about post-biopsy care per the written instructions.

Materials:

Equipment: sterile 5mm (or 6mm) Bergstrom biopsy cannula.

Supplies: 1 betadine 3-swab pack, commercial preps, or chlorhexidine solution
2 drape sheets
1 fenestrated drape sheet
1 laceration tray

- 1 lidocaine 1% w/o epinephrine (from Rx)
- 2pr sterile gloves
- 2 packs non-adhesive dressing sponges
- 1 Opti-lock IV extension tubing
- 1 sterile IV extension tubing ~24" long
- 1 #11 scalpel
- 1 Dermabond glue
- 2 clear Tegaderm-type dressing
- 1 50 or 60 mL syringe for suction
- 1 5mL syringe for rinsing muscle
- 1 18g needle for rinsing muscle
- 1 5mL sterile saline for rinsing muscle
- 2 6" ace bandage

Pre-Procedure:

1. Verify subject has already completed the consent and screening process.
2. Nurse verifies that subject has not taken any blood-thinning medications recently.
 - a. Prohibited medication classes: antiplatelet agents, anticoagulant agents. If subject uses these medications as prescribed by their physician, they will not be allowed to undergo a muscle biopsy.
 - b. Aspirin or aspirin-containing compounds: subjects should wait 7 days after the last dose of aspirin was ingested before they undergo a muscle biopsy.
3. Staff will set up a sterile field containing the above supplies and bx needle.
4. Explain the procedure to subject in terms that they understand, including expected sensations and side effects.

Procedure:

1. The biopsy site (lateral thigh, 1/2 way between hip and knee) will be prepped with one of the prep solutions to ensure disinfection.
2. Physician performing the bx and nurse will properly don sterile gloves.
3. The prepped area will be draped using the supplied sterile materials.

4. Sufficient 1% lidocaine solution will be used to anesthetize the skin, subcutaneous tissue and fascia at the biopsy site using supplied syringe and needles. Limit lidocaine volume to less than 20mL per biopsy. Wait approximately 6-10 minutes after the initial injection before testing area for sensation.
5. Using aseptic technique and sterile scalpel, a small incision (approximately ¼ inch) will be made in the skin after adequate anesthesia has been confirmed.
6. The Bergstrom needle will be inserted through the incision site approximately ¾ to 1" past the fascia, and a muscle biopsy will be taken with the aid of suction.
7. After the bx needle has been removed, a person wearing sterile gloves will apply firm compression for at least 7 minutes to the biopsy site.
8. Muscle sample will be handed to study staff for appropriate processing.
9. After hemostasis has been achieved, the biopsy site will be cleaned, and if this is the only or final biopsy to be performed, a medical adhesive will be used to close the incision. A pressure dressing will then be applied, and the subject will be advised to keep the pressure dressing on for approximately two hours.
10. The subject will be provided written wound care instructions, and these will be reviewed verbally as well.

Post Procedure and Discharge:

1. Provide subject with written wound care instructions and ensure they understand the instructions.
2. Call subject within 72 hours after the most recent bx to follow up for any problems or concerns.

Emergency Procedures and Adverse Event Reporting:

If bleeding persists, apply additional pressure to the site where muscle was biopsied. If necessary, apply ice pack to area to assist with hemostasis. Refer to study protocol for reporting procedures.

Documentation:

The study staff will complete the Muscle Biopsy Procedure note for each bx performed. Notes will be filed in the CRF.

